All patients in Part 1 of the study (i.e., Cohorts 1, 2, 3a-b, and 4a-d) will follow similar visit and assessments schedules. Selected assessments () will be optional for all enrolled patients at Sponsor-qualified sites. Other assessments (e.g., ABPM,) conducted for Cohorts 1 and 2 will not be conducted for patients in Cohorts 3 and 4. Following randomization, patients will be assessed in person during treatment at Weeks 1, 2, 4, 8, 12, and 16 and by telephone contact on Days 3, 10, and 21. Patients enrolling in Cohorts 3 and 4 will have additional assessments in person at Week 6 and additional telephone contact on Days 31, 38, and 49. Patients who do not enter Part 2 of the study (i.e., the extension period), either because they have discontinued taking study drug during Part 1 or have completed the 16-week treatment period as planned but chosen not to continue to Part 2 of the study, will complete an end-of-treatment visit when patient ends study drug. In addition a follow-up visit should occur four weeks after the date of administration of the last dose of study drug.

Part 2 (extension period):

Patients who discontinue treatment prematurely in study Part 1 are not eligible to continue into study Part 2. All patients from Part 1 who complete the 16-week treatment period as planned will be eligible to continue directly into the extension period to evaluate the intermediate and long-term safety and efficacy of bardoxolone methyl. Day 1 of the extension period will be the same as the Week 16 visit for the treatment period.

Cohort 1 and Cohort 2 patients randomized to placebo in Part 1 of the study will be assigned to receive bardoxolone methyl at their group-specific dose in the extension period. Patients enrolled in Cohorts 1 and 2 may dose titrate to the 10 mg dose or de-escalate at scheduled or unscheduled visits. However, patients who dose escalate must have a telephone call 1 week after

dose escalation and an unscheduled office visit or a home health visit 2 weeks (± 3 days) after dose escalation to collect clinical chemistry, BNP, and NT-Pro BNP.

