Cohorts 3 and 4 patients randomized to placebo in study Part 1 will be assigned to 5 mg of bardoxolone methyl, whereas, patients randomized to bardoxolone methyl in study Part 1 will begin study Part 2 (Week 16) at the same dose of bardoxolone methyl as they ended with in study Part 1. All patients in Cohorts 3 and 4 will have the option to up-titrate their dose at the Week 20 visit, and may de-escalate in dose (minimum dose of 2.5 mg) at scheduled or unscheduled visits. Treatment assignment will remain blinded for Cohort 3 and 4 patients through Week 20.

Treatment-compliant patients who have completed Part 2 of the study are eligible to continue receiving bardoxolone methyl through an extended access program (Study 402-C-1602). After Week 32, visits will occur every 24 weeks until bardoxolone methyl is available through the extended access program. Once bardoxolone methyl is available through the extended access program, patients in Part 2 who have completed at least 32 weeks of the study will complete an End of Treatment Visit. The Week 32 visit may be the same as the End of Treatment Visit. Beginning with the Week 32 visit, patients will be seen in the clinic every 24 weeks (i.e., Week 56, Week 80, Week 104, etc.) and receive a 6-month supply of study drug at the appropriate dose.

The Sponsor reserves the right to stop the study for a given cohort if development of bardoxolone methyl is discontinued for any reason, or if the assessment of available data raises concerns about the safety or efficacy of bardoxolone methyl.

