^a Total screening period should not exceed 60 days. If screening is longer than 28 days, BNP should be repeated through the central lab prior to randomization.

^b Study Day 1 is the day of administration of the first dose. **On Study Day 1, all procedures should be performed before study drug administration.**

^c Under the delegation of the Investigator and following Sponsor prior approval for each visit, a patient may be seen by a home health professional, qualified by documented training to perform study-specific procedures. If the visit is completed by home health professional, a limited physical assessment directed to assess for fluid retention and clinical worsening will be performed under the delegation of the Investigator

^d Patients who discontinue from the study prior to the Week 16 study visit will need to be brought back for all early termination assessments (i.e., both an end-of-treatment visit and then a follow-up visit 4 weeks after the date of administration of the last dose of study drug). Patients should complete the end-of-treatment procedures, including the 6MWT, prior to any adjustments being made to their PAH treatment regimen.

^e Screen A eligibility procedures do not need to be repeated on Day 1; however, a review of any changes in eligibility criteria should be evaluated prior to Day 1 procedures, and a urine pregnancy test should be performed for WOCBP.

- ^f Weights taken at home by the patient will begin on Day 2 and should be taken daily for the first 8 weeks and weekly thereafter, preferably at the same time each day and must be recorded in a diary and reviewed with the coordinator during telephone contacts and office visits.
- ^g If clinical worsening is suspected, further clinical evaluations may be required per Section 9.10.32.
- ^h A serum pregnancy test will be performed at Screen A for WOCBP or at any point in time if a pregnancy is suspected. All other pregnancy assessments will be urine pregnancy tests. Additional pregnancy assessments will be performed more frequently if required by local law or requested by local regulatory authorities or IRBs/ECs.
- ⁱ AE assessments on Day 1 should be done following study drug administration.

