Clinical chemistry ^j			X		X	X	X	X	X
BNP and NT-Pro BNP ^{l,k}			X		X	X	X ^k	X ^k	X
Hematology			X		X	X	X	X	X
Urinalysis and microscopy			X		X	X	X	X	X
6-min walk test					X	X	X	X	X
██████████					█	█	█	█	█
██████████						█		█	
Functional class assessment ^m						X		X	X
PK samples ⁿ					X				

^a All other Week 16 assessments will be completed as per Table 3 or Table 4.

^b Under delegation of the Investigator and with prior Sponsor approval, a patient may be seen by a home health professional. The home health professional must have documented study-specific training on file prior to the performance of any study-related procedures.

^c Visits beyond Week 32 will only occur until bardoxolone methyl is available through the extended access program. Once bardoxolone methyl is available through the extended access program, patients in Part 2 who have completed at least 32 weeks of the study will complete an End of Treatment Visit. If bardoxolone methyl is available through the extended access program prior to Week 32, the End of Treatment visit may coincide with the Week 32 visit.

^d Patients who are discontinued from the study during the extension period for any reason, including Sponsor termination of the study, and patients who are not participating in the extended access program must complete all end-of-treatment and follow-up visit assessments. Patients should complete the end-of-treatment assessments, including the 6MWT, prior to any adjustments being made to their PAH-specific treatment regimen.

- ^e Weights taken at home by the patient should be taken daily starting at week 16 through and including week 20 and weekly thereafter, preferably at the same time each day and must be recorded in a diary and reviewed with the coordinator during telephone contacts and office visits.
- ^f If clinical worsening is suspected, further clinical evaluations may be required per Section 9.10.32.
- ^g A limited physical assessment directed to assess for fluid retention and clinical worsening may be performed by a home health professional under the delegation of the Investigator
- ^h A serum pregnancy test will be performed at Screen A for WOCBP or at any point in time if a pregnancy is suspected. All other pregnancy assessments will be urine pregnancy tests. Additional pregnancy assessments will be performed more frequently if required by local law or requested by local regulatory authorities or IRBs/ECs.

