Functional class assessment ^l										X		X	X
PK samples ^m					X								
Pulmonary Function Testing	X				X					X		X	X
██████████	█				█					█		█	█

^a All other Week 16 assessments will be completed as per Table 3 or Table 4.

^b Under delegation of the Investigator and with prior Sponsor approval, a patient may be seen by a home health professional. The home health professional must have documented study-specific training on file prior to the performance of any study-related procedures.

^c Visits beyond Week 32 will only occur until bardoxolone methyl is available through the extended access program. Once bardoxolone methyl is available through the extended access program, patients in Part 2 who have completed at least 32 weeks of the study will complete an End of Treatment Visit. If bardoxolone methyl is available through the extended access program prior to Week 32, the End of Treatment visit may coincide with the Week 32 visit.

^d Patients who are discontinued from the study during the extension period for any reason, including Sponsor termination of the study, and patients who are not participating in the extended access program must complete all end-of-treatment and follow-up visit assessments. Patients should complete the end-of-treatment assessments, including the 6MWT, prior to any adjustments being made to their PAH-specific treatment regimen.

- e Weights taken at home by the patient should be taken daily starting at week 16 through and including week 20 and weekly thereafter, preferably at the same time each day and must be recorded in a diary and reviewed with the coordinator during telephone contacts and office visits.
- f If clinical worsening is suspected, further clinical evaluations may be required per Section 9.10.32.
- g A limited physical assessment directed to assess for fluid retention and clinical worsening may be performed by a home health professional under the delegation of the Investigator and with prior Sponsor approval.
- h A serum pregnancy test will be performed at Screen A for WOCBP or at any point in time if a pregnancy is suspected. All other pregnancy assessments will be urine pregnancy tests. Additional pregnancy assessments will be performed more frequently if required by local law or requested by local regulatory authorities or IRBs/ECs.

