9.1.1. Management of Fluid Status

Specific risk mitigation procedures will be employed to reduce the potential for bardoxolone methyl-induced fluid overload. These procedures include exclusion of patients with any clinically significant renal disease, defined as an eGFR value of < 45 mL/min/1.73 m². To exclude patients with significant cardiac dysfunction, the study will exclude patients with a history of left-sided heart disease. Patients who have evidence of volume overload at baseline, defined as BNP level of > 400 pg/mL, will also be excluded. Laboratory data will also be used to monitor fluid status after randomization.

Additionally, after randomization patients will be closely monitored for rapid weight gain suggestive of fluid overload. Patients will be given a Sponsor-provided scale to use at home to collect and record their weights daily during the first 4 weeks (Cohorts 1 and 2) or 8 weeks (Cohorts 3 and 4) of the treatment period and weekly thereafter. Patients who experience a five-pound (2.3 kilogram) or greater increase in weight since their Day 1 weight during Part 1 and during the first 4 weeks (Cohorts 1 and 2) or 8 weeks (Cohorts 3 and 4) of Part 2 will be instructed to stop taking their study medication immediately and return to the clinic for an unscheduled physical examination and laboratory assessment by the Investigator. Patients may not restart their study medication until the Investigator has completed and documented an assessment of fluid overload.

Investigators should also advise patients to watch for signs and symptoms of fluid overload. Patients should be informed to notify their physicians immediately if they experience swollen feet, chest pain, and shortness of breath with mild exertion or while lying down, or other relevant symptoms. The Investigator should immediately assess symptoms of fluid overload and determine appropriate medical management, as necessary, including whether stopping drug administration is required. At the earliest sign of worsening or new onset peripheral edema or other signs and symptoms of acute volume overload, Investigators will also be expected to determine if changes to a patient's diuretic regimen is needed.

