Since placebo patients will be transitioned to active treatment for the extension period (Part 2), and the blind will be maintained, all patients entering the extension will be closely monitored for weight gain just as they were monitored following randomization into the treatment period. Patients will use their Sponsor-provided scale during the first four weeks (Cohorts 1 and 2) or eight weeks (Cohorts 3 and 4) of the extension period and will record their weights daily. As in the treatment period (Part 1), patients will be instructed to stop taking their study medication immediately and return to the clinic for an unscheduled physical examination and laboratory assessment by the Investigator if they experience a five-pound or greater increase in weight since Week 16 (Day 1 of the extension period).

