9.10.8. Weight and Body Mass Index (BMI)

Weight should be measured at the times indicated in [Table 3](#) or [Table 4](#) and [Table 5](#) or [Table 6](#). Body mass index (BMI) will be calculated in the eCRF each time the weight is recorded. The Sponsor will provide each patient with a scale to use at home to capture daily weights. Weights should be taken at the same time each day and recorded in a patient diary. During the first four weeks (Cohort 1 and 2) or first eight weeks (Cohort 3 and 4) of both Part 1 and Part 2, weights will be collected daily; weekly weights will be collected thereafter. Patients will be instructed to stop administering study drug and contact the Investigator if their daily weight increases as per the criteria outlined in Section 9.1.1. Patients will be provided instructions within the Informed Consent Form to help ensure consistent weight collection throughout the study.

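### Table 6 ends daily home weights for Cohorts 3 and 4 at Week 20 of the extension, but Sections 9.1.1 and 9.10.8 require them to Week 24, after the Week 20 dose increase

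*Protocol*

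**What the plan says.** Four places in the protocol set the period of daily home weighing for Cohorts 3 and 4.

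- **Table 6, footnote e** (Part 2, Cohorts 3 and 4): "Weights taken at home by the patient should be taken daily starting at week 16 through and including week 20 and weekly thereafter".
- **Section 9.1.1**, on the extension: "eight weeks (Cohorts 3 and 4) of the extension period and will record their weights daily". The five-pound rule has the same window: "8 weeks (Cohorts 3 and 4) of Part 2 will be instructed to stop taking their study medication immediately".
- **Section 9.10.8**: "first eight weeks (Cohort 3 and 4) of both Part 1 and Part 2, weights will be collected daily". This section also refers the reader to Table 6 for timing.
- **Table 4, footnote f** (Part 1, same cohorts): home weights "should be taken daily for the first 8 weeks and weekly thereafter".

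For Cohorts 1 and 2, Table 5 footnote e says home weights "should be taken daily starting at week 16 through and including week 20 and weekly thereafter". That agrees with the four weeks that Sections 9.1.1 and 9.10.8 give those cohorts.

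On dosing in Part 2, Section 7.1 states: "All patients in Cohorts 3 and 4 will have the option to up-titrate their dose at the Week 20 visit". Former placebo patients in these cohorts start 5 mg at Week 16.

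**The concern.** Site staff usually work from the schedule table. Staff who follow Table 6 would move patients to weekly home weights at the visit where the dose may be raised, or one week later. Sections 9.1.1 and 9.10.8 would keep daily weights for four weeks after that visit.

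Home weights are not just descriptive data here. Patients apply the five-pound threshold to their own readings and stop study drug if they cross it, and for Cohorts 3 and 4 that rule runs to Week 24. Section 5.1.2 reports that heart failure in the earlier trial in Stage 4 CKD was often preceded by rapid fluid weight gain. With weekly weights, a threshold crossing could go unseen for several days between contacts.

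**Working it through.** **Inputs.** Nominal study days from SAP Tables 1 and 2: Week 4 = 28, Week 8 = 56, Week 16 = 112, Week 20 = 140, Week 24 = 168. Extension Day 1 is the Week 16 visit (Section 7.1). Visit windows are ignored at first.

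**Step 1. Reproduce the requirement in the text.** 168 − 112 = 56 days, which is the eight weeks of Sections 9.1.1 and 9.10.8. Of these, 168 − 140 = 28 days follow the Week 20 visit. Part 1 gives the same cover after the Week 4 escalation: 56 − 28 = 28 days.

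**Step 2. Apply footnote e.** Its end point can be read in two ways.

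| | Sections 9.1.1 and 9.10.8 | Reading A: ends at the Week 20 visit (day 140) | Reading B: ends seven days later (day 147) |
|---|---|---|---|
| Days of daily weighing | 56 | 140 − 112 = 28 | 147 − 112 = 35 |
| Daily weighing lost | 0 | 168 − 140 = 28 (28/56 = 50%) | 168 − 147 = 21 (21/56 = 37.5%) |
| Daily weighing after Week 20 | 28 | 0 | 147 − 140 = 7 |
| Weekly home weights in the lost period | – | 4 | 3 |
| Net home readings lost | 0 | 28 − 4 = 24 | 21 − 3 = 18 |
| Days with any scheduled weight, Weeks 20 to 24 | 28 | 4 to 6 | 10 to 12 |

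The ranges in the last row depend on whether the clinic weights at Weeks 22 and 24 fall on separate days from the home weights: A = 4 + (0 to 2); B = 7 + 3 + (0 to 2). Counting day 112 as the first day changes the 28 lost days to 27 and leaves 21 unchanged.

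**Step 3. Decide which text is the outlier.** The footnote has the same wording as Table 5 footnote e. The Part 1 table for Cohorts 3 and 4, the stop rule and both text sections all give eight weeks. Elsewhere the protocol adds contacts for these cohorts after a possible dose increase. In Part 1 they have "additional assessments in person at Week 6 and additional telephone contact on Days 31, 38, and 49". In Part 2, Table 6 adds calls at Weeks 21 and 23 and visits at Weeks 22 and 24 that Table 5 does not have. Only footnote e breaks this pattern, so a carry-over from Table 5 is the likeliest explanation.

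**Step 4. Count the patients affected (upper limits).** Section 7.2 gives six subcohorts: 6 × 24 = 144 as planned and 6 × 72 = 432 at the maximum, if all enter Part 2. No dose above 10 mg is named for these cohorts. If 10 mg is the ceiling (an assumption), up-titration at Week 20 concerns mainly former placebo patients. Under 2:1 allocation that is one third, so up to 48 planned or 144 at the maximum. Patients held or reduced below 10 mg in Part 1 would add to this. How many would up-titrate is unknown.

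**Step 5. The related conflict in Section 7.3.** That section rules out intra-patient escalation for Cohorts 1 and 2 in both parts. The Synopsis and Section 7.1 allow those patients to titrate to 10 mg in Part 2, Table 5 footnote i sets follow-up after an escalation, and Section 9.7 lists unscheduled visits for it. The last sentence of Section 7.3 also limits extension escalation to Week 20 for all patients, which does not fit Cohorts 1 and 2 either. At most 38 + 16 = 54 planned patients are concerned, fewer once those already at 10 mg or above, or not entering Part 2, are removed.

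**The case against.** The contradiction itself is hard to dispute, but there is a fair case that it matters little.

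- **The loss is conditional.** It occurs only where a site follows the footnote over two text sections. Patient instructions are in the consent form, which is not available here, so what patients were told is unknown. This stands.
- **Monitoring continues.** Table 6 keeps weekly home weights, diary review at each of Weeks 21 to 24, and visits with weight, BNP and a physical examination or clinical worsening assessment at Weeks 22 and 24. The calls ask about weight and fluid retention, and patients are told to report symptoms at once. The five-pound rule counts from Week 16, so a weekly weight can still trigger it. This stands: what is lost is day-to-day detection between contacts.
- **The documented risk period is covered.** Section 5.1.2 places the excess fluid risk in the first three to four weeks of treatment. Table 6 gives former placebo patients daily weights over that period. Excess risk after a dose increase is an assumption. This stands, although the protocol itself asks for extra follow-up after a dose increase.
- **Not every lost day must follow up-titration.** With the ±3-day window, a late Week 20 visit could put up to three of them before it, if the site stops daily weights on day 140. This is a small qualification.
- **A narrower rule is possible.** Section 9.1.1 justifies close monitoring by the placebo patients' move to active drug under the blind, and the blind ends at Week 20. Daily weights after Week 20 only for those who up-titrate would be defensible. But that would mean rewriting Sections 9.1.1 and 9.10.8, and nothing suggests the sponsor chose it.

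These points limit the consequence. None reconciles the two instructions.

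**Conclusion.** The point holds. Footnote e of Table 6 is wrong as written for Cohorts 3 and 4, and it bears on a working safety rule. On nominal days, a site following it gives up 28 or 21 of the 56 days of daily weighing that the text requires, all after the Week 20 visit. Weekly weights partly fill the gap, leaving 24 or 18 fewer home readings per patient.

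The size rests on the two readings of the end point, on nominal visit timing and on sites using the table. Any clinical effect further assumes that a dose increase raises fluid risk, which the documents do not show. This should be corrected, but it does not threaten the trial's conclusions, and the Part 1 comparison is untouched.

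The Section 7.3 conflict is also real, but a site that follows the stricter sentence simply does not escalate. Its effect is inconsistent Part 2 dosing between sites, not a loss of safety.

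**What to change.** - **Table 6, footnote e:** require daily home weights from Week 16 up to and including Week 24, then weekly. This brings the table into line with Sections 9.1.1 and 9.10.8 and with the stop rule.
- **Section 7.3:** limit the ban on intra-patient escalation in Cohorts 1 and 2 to Part 1. In the same edit, restrict the final sentence on Week 20 escalation to Cohorts 3 and 4.
- **Sites:** send a short memo, and check that the weighing instructions in the consent form agree.

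The cost is two small text edits and the memo. Each Cohort 3 or 4 patient would have 21 to 28 more days of daily home weighing than Table 6 now asks for, on a scale already supplied. No visits or tests are added. The footnote correction does not depend on the Section 7.3 edits.

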8. SELECTION AND WITHDRAWAL OF PATIENTS

8.1. Patient Inclusion Criteria

Diagnosis and main criteria for inclusion:

1. Adult male and female patients ≥ 18 to ≤ 75 years of age upon study consent;
2. BMI > 18.5 kg/m²;
3. Symptomatic pulmonary hypertension WHO Functional Class II and III;
4. WHO Group I, III, or V PH according to the following criteria:
 - a. If diagnosed with WHO Group I PAH, then one of the following subtypes:
 - i. Idiopathic or heritable PAH;
 - ii. PAH associated with connective tissue disease;
 - iii. PAH associated with simple, congenital systemic-to-pulmonary shunts at least 1 year following shunt repair;
 - iv. PAH associated with anorexigen or drug-induced toxicity;
 - v. PAH associated with human immunodeficiency virus (HIV); or
 - b. If WHO Group III PH, then primary diagnosis must be one of the following subtypes:
 - i. Connective tissue disease associated ILD (CTD-ILD);
 - ii. Idiopathic pulmonary fibrosis (IPF), according to the American Thoracic Society and European Respiratory Society (ATS/ERS) guidelines ([Raghu 2011](#));
 - iii. Nonspecific interstitial pneumonia (NSIP) or the following idiopathic interstitial pneumonia subtypes, according to the American Thoracic Society and European Respiratory Society (ATS/ERS) guidelines ([Travis 2013](#)):
 1. Respiratory bronchiolitis-associated interstitial lung disease;
 2. Desquamative interstitial pneumonia;
 3. Cryptogenic organizing pneumonia;
 4. Acute interstitial pneumonitis;
 5. Idiopathic lymphoid interstitial pneumonia;
 6. Idiopathic pleuroparenchymal fibroelastosis;
 7. Unclassifiable idiopathic interstitial pneumonia, including patients who have not had a lung biopsy; or
 - c. If WHO Group V PH, then patient must be diagnosed with sarcoidosis;

5. Had a diagnostic right heart catheterization performed and documented prior to Day 1 that confirmed a diagnosis of PH according to all the following criteria:
 - a. If diagnosed with WHO Group I PAH, then:
 - i. Mean pulmonary artery pressure ≥ 25 mm Hg (at rest);
 - ii. Pulmonary capillary wedge pressure (PCWP) ≤ 15 mm Hg;
 - iii. Pulmonary vascular resistance > 240 dyn.sec/cm⁵ or > 3 mm Hg/Liter (L)/minute;
 - b. If not diagnosed with WHO Group I PAH, then:
 - i. Mean pulmonary artery pressure ≥ 21 mm Hg (at rest);
 - ii. Pulmonary capillary wedge pressure (PCWP) ≤ 15 mm Hg;
 - iii. Pulmonary vascular resistance > 160 dyn.sec/cm⁵;
6. Has BNP level ≤ 400 pg/mL;
7. Has an average 6-minute walk distance (6MWDs) ≥ 150 meters on two consecutive tests performed on different days prior to randomization, with both tests measuring within 15% of one another;
8. Has been receiving no more than two (2) approved disease-specific PAH therapies. Cohort 3b WHO Group I PAH patients enrolled outside the United States must be receiving zero (0) or one (1) PAH therapies. PAH therapy must be at a stable dose for at least 90 days prior to Day 1;
9. If WHO Group III or WHO Group V, disease-specific therapy must be at a stable dose for 30 days;
10. Has maintained a stable dose for 30 days prior to Day 1 if receiving any of the following therapies that may affect PH: vasodilators (including calcium channel blockers), digoxin, L-arginine supplementation, or oxygen supplementation;
11. If receiving prednisone, has maintained a stable dose of ≤ 20 mg/day (or equivalent dose if other corticosteroid) for at least 30 days prior to Day 1. If receiving treatment for connective tissue disease (CTD) with any other drugs, doses should remain stable for the duration of the study;
12. Had pulmonary function tests (PFTs) within 90 days prior to Day 1 that meet the following criteria:
 - a. For WHO Group I PAH patients with connective tissue disease, total lung capacity (TLC) $\geq 65\%$ (predicted);
 - b. For all other WHO Group I PAH patients,
 - i. Forced expiratory volume in 1 second (FEV1) $\geq 65\%$ (predicted); or
 - ii. FEV1/forced vital capacity ratio (FEV1/FVC) $\geq 65\%$;
 - c. For WHO Group III or V PH patients, total lung capacity (TLC) between 50-90% (predicted);

13. For WHO Group I patients, had a ventilation-perfusion (V/Q) lung scan or spiral/helical/electron beam computed tomography (CT) or pulmonary angiogram prior to Screening that shows no evidence of thromboembolic disease (i.e., should note normal or low probability for pulmonary embolism). If V/Q scan was abnormal (i.e., results other than normal or low probability), then a confirmatory CT or selective pulmonary angiography must exclude chronic thromboembolic disease;
14. Has adequate kidney function defined as an estimated glomerular filtration rate (eGFR) ≥ 45 mL/min/1.73 m² using the Modification of Diet in Renal Disease (MDRD) 4-variable formula;
15. Willing and able to comply with scheduled visits, treatment plan, laboratory tests, and other study procedures;
16. Evidence of a personally signed and dated informed consent document indicating that the patient (or a legally acceptable representative) has been informed of all pertinent aspects of the study prior to initiation of any patient-mandated procedures;
17. For WHO Group III or V PH patients, the presence of ILD must be confirmed by a diagnostic high resolution computed tomography (HRCT) scan or biopsy performed and documented prior to Day 1.

